11.1.2 Other significant adverse events

During the evaluation of the AE data, an AstraZeneca medically qualified expert will review the list of AEs that were not reported as SAEs and discontinuation of IP due to AEs. Based on the expert's judgment, significant AEs of particular clinical importance may, after consultation with the Global Patient Safety Physician, be considered other significant AEs (OAEs) and reported as such in the CSR. A similar review of laboratory, vital sign, and other safety data will be performed for identification of OAEs.

Examples of these are marked hematological and other laboratory abnormalities, and certain events that lead to intervention (other than those already classified as serious), dose reduction, or significant additional treatment.

11.2 Calculation or derivation of pharmacokinetic variables

The PK analyses of the plasma concentration data for AZD9291 and its metabolites will be performed at

standard operating procedures (SOPs) and Work Instructions will be used as the default methodology if not otherwise specified.

The actual sampling times will be used in the final PK parameter calculations. Nominal sampling times will be used for interim PK parameter calculations.

Pharmacokinetic parameters will be derived using noncompartmental methods with Phoenix[®] WinNonlin[®] Professional Version 6.3, or higher,

and/or SAS[®] Version 9.2, or higher

. All descriptive and inferential statistical computations will be performed using SAS Version 9.2, or higher.

Where possible the following PK parameters will be determined for AZD9291 and its metabolites, AZ5104 and AZ7550, as appropriate:

- Maximum plasma concentration (C_{\max})
- Time to C_{\max} (t_{\max})
- Terminal rate constant (λ_z)
- Terminal half life ($t_{1/2,\lambda_z}$)
- Lag time before observation of quantifiable analyte concentrations in plasma (t_{lag})
- Area under the plasma concentration-time curve from zero to the time of the last measurable concentration [$AUC_{(0-t)}$]
- Area under the plasma concentration-time curve from zero to 72 hours [$AUC_{(0-72)}$]
- Area under the plasma concentration-time curve from zero to infinity (AUC)
- Apparent plasma clearance (CL/F) for AZD9291 only
- Apparent volume of distribution (V_z/F) for AZD9291 only
- Parent to metabolite ratio (calculated as AZD9291/AZ5104 and AZD9291/AZ7550 for both C_{\max} and AUC). These ratios will be adjusted for differences in molecular weight (AZD9291 = 499.62; AZ5104 and AZ7550 = 485.59).

Additional parameters may also be calculated, if appropriate.

12. STATISTICAL METHODS AND SAMPLE SIZE DETERMINATION

12.1 Description of analysis sets

12.1.1 General principles

The analysis of data will be based on different subsets according to the purpose of analysis, ie, for safety and PK, respectively.

12.1.2 Safety analysis set

All volunteers who received at least 1 dose of IP and for whom any postdose data are available will be included in the safety population.

12.1.3 Pharmacokinetic analysis set

The PK analysis set will be a subset of the safety analysis set and will include only volunteers who receive at least 1 dose of IP and have at least 1 postdose PK measurement without important CSP deviations or significant events thought to significantly affect the PK (eg, volunteer vomited at or before 2 times median t_{\max} , wrong dose administered, prohibited concomitant medication, etc).

12.2 Methods of statistical analyses

12.2.1 General principles

The PK and safety summaries, individual figures, and data listings, as well as the statistical analysis of PK variables will be the responsibility of the study biostatistician at using SAS[®] Version 9.2 or higher and, where appropriate, additional validated software.

Quantitative continuous variables will be summarized using descriptive statistics, including n, mean, standard deviation (SD), median, minimum, and maximum values. Additionally, for PK parameters, (except for t_{\max}), geometric means and geometric coefficient of variation (CV) will be reported. The geometric mean is calculated as the exponential of the arithmetic mean calculated from data on a log scale. The CV is calculated as $100 \cdot \sqrt{(\exp(s^2) - 1)}$ where s is the SD of the data on a log scale. Mean, SD, geometric mean, and CV will not be calculated for t_{\max} .

Categorical variables (eg, gender) will be summarized in frequency tables (frequency and proportion of volunteers in the analysis set).

In general, descriptive statistics will follow the rounding convention in SOPs.

Baseline characteristics will be summarized across all volunteers.

12.2.2 Subject characteristics

Continuous variables will be summarized using descriptive statistics (n, mean, SD, minimum, median, and maximum) and categorical variables will be summarized in frequency tables (frequency and proportion) for all volunteers overall.

12.2.3 Safety

All safety data (scheduled and unscheduled) will be presented in the data listings.

Safety variables (eg, clinical laboratory values and vital signs) will be reported to the same precision as the source data. Derived variables will be reported using similar precision to those from which they were derived (eg, QTcF derived from QT interval).

Extra measurements (such as unscheduled or repeat assessments) will not be included in the descriptive statistics by scheduled time point, but will be included in data listings. All AEs and clinical laboratory outliers that occur following the first dose of study medication will be included in the tabulations of AEs and outlier events, including episodes that occur at unscheduled evaluations.

All available data from volunteers in the safety analysis set will be included in the safety analyses. No adjustment or imputation will be utilized for missing values or for volunteers who withdraw prior to completing the study, neither will analyses be restricted to volunteers with complete data.

Adverse events beginning at or after the first dose of IP will be summarized by preferred term and system organ class using MedDRA vocabulary by treatment and across all treatments. Adverse events that begin during the washout periods will be assigned to the last treatment received prior to the onset of the AE. Furthermore, listings of SAEs and AEs that lead to withdrawal will be made and the number of volunteers who have any AEs, SAEs, AEs that lead to withdrawal, and AEs with severe intensity will be summarized.

Tabulations and listings of data for vital signs, clinical laboratory tests, ECGs, and physical and ophthalmologic examination findings will be presented, as appropriate. All continuous safety data will be summarized by treatment and/or across all treatments, as appropriate, for the observed value at each scheduled assessment and for the corresponding change from baseline. For clinical laboratory tests, listings of values for each volunteer will be presented with abnormal or out-of-range values flagged. Clinical laboratory data will be reported in Système International units in the CSR.

12.2.4 Pharmacokinetics

The PK blood sample collection times, as well as derived sampling time deviations, and plasma concentrations of each analyte will be listed for all volunteers. Plasma concentrations will be summarized by treatment using descriptive statistics (eg, n, arithmetic mean, SD, minimum, median, maximum, geometric mean, and CV). Individual concentration versus time profiles will be prepared.

Plasma concentrations that are below the lower limit of quantitation (LLOQ) will be handled as follows:

- At a time point where less than or equal to 50% of the values are below the limit of quantitation (BLQ), all BLQ values will be set to LLOQ, and all descriptive statistics will be calculated.
- At a time point where more than half of the values are BLQ, the mean, SD, geometric mean and CV will be set to Not Determined. The maximum value will be reported from the individual data, and the minimum and median will be set to BLQ.

- If all values are BLQ at a time point, no descriptive statistics will be calculated for that time point. Not applicable will be reported for SD and CV, and BLQ will be reported for mean, geometric mean, minimum, median, and maximum.
- The number of BLQ values (n below LLOQ) will be reported for each time point.

Plasma parameters for all analytes will be summarized by treatment using descriptive statistics (eg, n, arithmetic mean, SD, minimum, median, maximum, geometric mean, and CV). For t_{\max} , only n, median, minimum, and maximum will be reported. Individual and geometric mean C_{\max} , $AUC_{(0-t)}$, and AUC will be presented graphically.

Data from volunteers excluded from the PK analysis set will be included in the data listings, but not in the summaries.

Part A

The bioavailability of the 20-mg solution and that of the 20-mg tablet relative to the 20-mg capsule will be assessed using the primary PK variables AUC and/or $AUC_{(0-t)}$ and C_{\max} of plasma AZD9291. These endpoints will be natural log-transformed and analyzed using a linear mixed effects model with fixed effect for treatment and random effect for subject. The difference in treatment (formulation) means will be determined along with its associated 90% confidence interval (CI) and back-transformed to give an estimate of the relative bioavailability. The results of this analysis will be presented in terms of geometric means for both treatments, the relative bioavailability (ie, the ratio of the treatment formulation geometric means) and its 90% CI.

The above treatment comparisons will also be performed for t_{\max} as secondary analyses. Nonparametric methods will be used to compute median t_{\max} for each treatment, median t_{\max} difference, and associated 90% CI for the median difference. The data will be analyzed by a Wilcoxon Signed-Rank Test. The 90% CI will be calculated using the method of Hahn and Meeker (Hahn and Meeker 1991).

Similar statistical analyses may be performed for AZ5104 and AZ7550 if appropriate.

For the bioavailability analyses, if there are more than 20% healthy volunteers whose AUCs are not calculable for either treatment due to large residual area (>20%), $R_{sq} < 0.80$ or any other reason, $AUC_{(0-t)}$ will also be analyzed statistically and presented in the same way as AUC. Otherwise, $AUC_{(0-t)}$ will not be statistically analyzed.

All volunteers receive treatments in the same order and so results may be confounded with undetectable period effects, which will be considered in interpretation.

Part B

For the investigation of the effect of food, the primary PK variables AUC and/or $AUC_{(0-t)}$ and C_{\max} of plasma AZD9291 will be analyzed. These endpoints will be natural log-transformed and analyzed using a linear mixed effects model with fixed effect for treatment and random

effect for subject. The difference in treatment means will be determined along with its associated 90% CI and back-transformed to give an estimate of the effect of food on the exposure of AZD9291. The results of this analysis will be presented in terms of geometric means for both treatments, the effect of food on the exposure of AZD9291 (ie, the ratio of the treatment geometric means) and its 90% CI. Similar statistical analyses may be performed for AZ5104 and AZ7550, if appropriate.

For the investigation of the effect of food, if there are more than 20% healthy volunteers whose AUCs are not calculable for either treatment due to large residual area (>20%), $R_{sq} < 0.80$ or any other reason, $AUC_{(0-t)}$ will also be analyzed statistically and presented in the same way as AUC. Otherwise, $AUC_{(0-t)}$ will not be statistically analyzed.

All volunteers receive treatments in the same order and so results may be confounded with undetectable period effects, which will be considered in interpretation.

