after the last dose of AZD9291 (up to 7 days after completion of Period 2). During the study, each volunteer will receive a single, 20-mg dose of AZD9291 on 2 separate occasions.

Outcome variable(s):

- Pharmacokinetics
 - AZD9291 and AZ5104 and AZ7550 (AZD9291 metabolites) plasma concentrations will be used to assess the following parameters, as applicable: AUC, AUC₍₀₋₇₂₎, AUC_(0-t), C_{max}, t_{1/2,λz}, λ_z, t_{max}, t_{lag}, CL/F (AZD9291 only), and V_z/F (AZD9291 only), and parent to metabolite ratio (calculated as AZD9291/AZ5104 and AZD9291/AZ7550 for both C_{max} and AUC) (Part A and Part B).
 - The primary variables for assessments of relative bioavailability are AZD9291 C_{max}, AUC, and/or AUC_(0-t) (Part A).
 - The secondary variable for assessment of relative bioavailability is t_{max} (Part A).
 - The primary variables for assessment of food-effect are AZD9291 C_{max}, AUC, and/or AUC_(0-t) (Part B).
 - The secondary variable for assessment food-effect is t_{max} (Part B).
- Safety (secondary endpoints)

Safety parameters include adverse events, vital signs, physical examinations, ophthalmologic examination, electrocardiograms, and clinical laboratory assessments (Part A and Part B).

Statistical methods

Part A

Inferential statistical analyses will be performed on the pharmacokinetic data only. The bioavailability of the 20-mg solution and a 20-mg tablet relative to the 20-mg capsule will be assessed using the primary pharmacokinetic variables, C_{max}, AUC, and/or AUC_(0-t), of plasma AZD9291. These endpoints will be natural log-transformed and analyzed using a linear mixed effects model. The difference in treatment (formulation) means will be determined along with its associated 90% confidence interval and back-transformed to give an estimate of the relative bioavailability. The results of this analysis will be presented in terms of geometric means for each treatment, the relative bioavailability (ie, the ratio of the treatment formulation geometric means) and its 90% confidence interval.

The above treatment comparisons will also be performed for t_{max} as the secondary analyses. Nonparametric methods will be used to compute median t_{max} for each treatment, median t_{max} difference, and associated 90% confidence interval for the median difference. The data will

be analyzed by a Wilcoxon Signed-Rank Test. The 90% confidence interval will be calculated using the method of Hahn and Meeker (Hahn and Meeker 1991).

Part B

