Blood samples for the determination of AZD9291 and metabolite (AZ5104 and AZ7550) concentrations will be collected prior to dosing and serially postdose through Day 22 in each treatment period. Safety assessments will include monitoring of AEs and concomitant medications; clinical laboratory tests (hematology, clinical chemistry, and urinalysis); measurement of vital signs; electrocardiograms (ECGs); physical examinations; screening for drugs of abuse, alcohol, and cotinine; and ophthalmologic examinations. The PK profile from 0 to 72 hours postdose will be assessed after Periods 1, 2 and 3, and any volunteer with exposures exceeding the PK limits (see Section 5.8) will be withdrawn and may be replaced if required to ensure 12 evaluable volunteers complete the bioavailability assessment.

A study flow chart is shown in Figure 1. The overall study plan and schedule of assessments are presented in Table 1 and Table 3.

Part B

Part B will be a fixed-sequence, 2-period, study design to assess the effect of food on AZD9291. Approximately 16 healthy male volunteers aged 18 to 55 years (inclusive) will be enrolled to ensure 12 completers.

This study will consist of 2 treatment periods during which the following treatments will be administered.

- Period 1: A single 20-mg oral AZD9291 dose under fasted conditions on Day 1.
- Period 2: A single 20-mg oral AZD9291 dose under fed conditions on Day 1.

The 2 treatment periods will be separated by a washout of at least 21 days (from the first AZD9291 administration in Period 1 until the first AZD9291 administration in Period 2)

Based on the bioavailability results from Part A, Part B may be conducted either with the tablet formulation or with the capsule formulation. All volunteers will receive a single, oral dose of 20-mg AZD9291 along with 240 mL water while in an upright position following an overnight fast of 10 hours in Period 1, and a single oral dose of 20-mg AZD9291 along with 240 mL water in the fed state (following a high-fat breakfast) in Period 2.

Part B will consist of 4 visits (for details and timing of assessments see Table 2 and Table 4). The screening visit (Visit 1) will be conducted within 28 days of Visit 2. Following fully written informed consent, healthy volunteers will be enrolled into the study and screened for eligibility.

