12.3 Determination of sample size

No formal sample size calculation has been performed as the number of volunteers in each sequence has been chosen to ensure sufficient data are collected while minimizing exposure to a new drug. There are no within-subject data available to enable an estimate of sample size based on within-subject variability. Based on consideration of information provided in Food and Drug Administration guidances (FDA 2002, FDA 2003), the sample size has been selected with the aim of ensuring a minimum of 12 evaluable volunteers complete for both study parts.

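### Below the 20% trigger the protocol bars an AUC(0-t) ratio, so the only extent-of-exposure ratio with a 90% CI may rest on volunteers whose AUC could be extrapolated

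*Protocol*

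**What the plan says.** The synopsis (Outcome variables) states: "The primary variables for assessments of relative bioavailability are AZD9291" Cmax, AUC and/or AUC(0-t). Section 12.2.4 repeats this for Part A, where relative bioavailability "will be assessed using the primary PK variables AUC and/or" AUC(0-t), together with Cmax. Part B uses the same set for the food effect.

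Section 12.2.4 then makes the AUC(0-t) analysis conditional, in the same terms for each part. It is done "if there are more than 20% healthy volunteers whose AUCs are not calculable for either treatment due to large residual area (>20"%), Rsq below 0.80 or any other reason. Failing that, AUC(0-t) "will not be statistically analyzed".

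The analysis is a "linear mixed effects model with fixed effect for treatment and random effect for subject" on the log scale, giving a ratio with a 90% CI. The same section has plasma parameters summarised by treatment with geometric means and CVs, and AUC(0-t) plotted individually and as geometric means.

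On numbers, Section 12.3 says "No formal sample size calculation has been performed" and that "the sample size has been selected with the aim of ensuring a minimum of 12 evaluable volunteers complete for both study parts". Section 3.1 says of Part B: "Approximately 16 healthy male volunteers aged 18 to 55 years (inclusive) will be enrolled to ensure 12 completers". Part A has the same target.

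**The concern.** AUC to infinity needs a usable terminal slope and a small extrapolated area. A volunteer who fails either test has no AUC in that period. The residual fraction is Clast/(λz × AUC), so failure is more likely when elimination is slow or when concentrations fall below quantification early. Those features can differ between formulations or between fed and fasted dosing, so the missing AUCs need not be a random subset.

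AUC(0-t) needs no extrapolation and can usually be obtained for the same volunteers, yet the protocol rules out comparing it formally while the number of missing AUCs stays at or below the trigger. The reader then has an AUC ratio based on a selected group and no extent-of-exposure ratio with an interval in everyone to set beside it. In Part A this ratio is part of the primary objective, and Part A results choose the formulation for Part B. Because the protocol itself states the prohibition, this is not a detail it leaves to the SAP.

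**Working it through.** There is no powered sample size to reproduce. The checks are where the trigger falls, how likely it is that AUCs are missing without reaching it, and what that would cost.

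**1. Where the trigger falls.** Inputs: more than 20% (Section 12.2.4), 12 evaluable (Section 12.3), about 16 enrolled (Section 3.1). The largest k with k/n ≤ 0.20 is:

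- n = 12: 2/12 = 16.7% does not trigger; 3/12 = 25% does.
- n = 15: 3/15 is exactly 20%, which is not more than 20%, so it does not trigger.
- n = 16: 3/16 = 18.75% does not trigger; 4/16 = 25% does.

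This counts each volunteer once. The rule speaks of either treatment, which can also be read as a separate count per treatment. Two volunteers could then lack AUC on one treatment and two others on the second: 2 + 2 = 4 of 12 in a two-treatment comparison without triggering. Part A has three treatments, so the wording is less clear still.

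**2. How likely a large residual area is.** Inputs: last sample at 504 h (Tables 3 and 4); half-life 30 to 110 h, median 50 h (Sections 1.1 and 3.2). Assuming mono-exponential decline, residual fraction = exp(−ln 2 × t_last / t½).

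| Half-life (h) | Last quantifiable at 216 h | 336 h | 504 h |
|---|---|---|---|
| 50 | 5.0% | 0.9% | 0.1% |
| 110 | 25.6% | 12.0% | 4.2% |

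The residual exceeds 20% when t_last < t½ × ln 5 / ln 2, or about 2.3 half-lives. With a quantifiable 504 h sample, that needs a half-life above 504 × ln 2 / ln 5 = 217 h, about twice the longest reported. At 110 h it needs the last quantifiable sample before about 255 h, which on this schedule means 216 h or earlier.

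**3. Chance of falling in the gap.** If each volunteer independently has probability p of a non-calculable AUC (assumed), P(1 or 2 of 12) = 12p(1−p)^11 + 66p²(1−p)^10:

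- p = 2%: 0.21
- p = 5%: 0.44
- p = 10%: 0.61

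**4. Effect on the point estimate.** Suppose k of n volunteers contribute nothing and their individual ratio is r times that of the others (r assumed). The full-sample geometric mean ratio then differs from the reported one by r^(k/n). For 2 of 12:

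- r = 1.25: 1.25^(1/6) = 1.038, about 4%
- r = 1.5: 1.5^(1/6) = 1.070, about 7%
- r = 2: 2^(1/6) = 1.122, about 12%

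**5. Effect on precision.** 90% CI around a ratio of 1 = exp(± t(0.95, n−1) × s × √(2/n)), with s = √ln(1 + CV²). Section 12.3 says no within-subject data exist, so the CV is assumed.

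| Assumed CV | n = 10 | n = 12 |
|---|---|---|
| 20% | 0.850 to 1.176 | 0.865 to 1.156 |
| 30% | 0.786 to 1.272 | 0.806 to 1.240 |

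The loss of precision is small. Any harm lies mainly in which volunteers are missing.

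**The case against.** The case for leaving the rule alone has several sound parts.

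- A reader might infer that below the trigger there is no exposure comparison in all volunteers. The protocol does not support that. Cmax is a primary variable and is modelled with a 90% CI whatever happens to AUC. By-treatment summaries and plots of AUC(0-t) would give some sign of a shift. What they lack is a within-subject ratio with an interval.
- A reader might also infer that the data choose which primary variable exists. In fact AUC(0-t) is added to AUC when the trigger is met and does not replace it. The threshold is numerical and fixed in advance, and Section 12.2.4 gives no acceptance limits, so no pass or fail result turns on it.
- Nor do affected volunteers necessarily leave the analysis. No complete-case restriction is stated, and the random subject effect keeps a volunteer with another calculable AUC in the model. He adds little to the within-subject contrast, however, and the random effect does not remove bias if missingness depends on the unobserved AUC itself.
- On the reported half-lives, a residual above 20% is improbable with sampling to 504 h. This stands, with limits. Section 3.2 says 19 of 24 patients were sampled only to 72 h, and Section 1.1 itself cautions that half-life was poorly characterised. The protocol gives no LLOQ. Rsq below 0.80 or missed outpatient samples are other routes to a missing AUC, though nothing shows that these depend on formulation or food.
- AUC(0-t) is not a perfect substitute, since its end time can differ between treatments, perhaps most in the volunteers at issue. That supports a supportive role for it but not a ban on analysing it.

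**Conclusion.** The point holds as a minor one. In both parts, with up to 2 of 12 or 3 of 16 volunteers lacking AUC (up to 4 of 12 on a per-treatment count), the only inferential extent-of-exposure ratio depends on those with calculable AUC, a selection that may follow the terminal phase. No AUC-type ratio with a 90% CI then covers all evaluable volunteers.

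The 4% to 12% shift is illustrative. It assumes that two volunteers contribute nothing and that their ratio differs 1.25- to 2-fold; the protocol supplies neither figure. The probabilities of 0.21 to 0.61 likewise rest on assumed failure rates. The documents do not show that the primary result will be biased, only that the rule withholds an inexpensive check on it.

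**What to change.** In Section 12.2.4, delete the 20% condition and the prohibition for both parts. Name AUC and Cmax as primary in that section and in the synopsis, replacing the and/or wording. Always report the AUC(0-t) ratio with its 90% CI, from the same mixed model, as a standing supportive analysis. This also removes the question of how to count either treatment.

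AUC(0-72) could be added as an option. Section 11.2 already lists it for derivation, Section 5.8 uses it for the PK limits, and it has a common end time. It captures only part of exposure, though: under mono-exponential decline, 1 − exp(−ln 2 × 72/50) = 63% at a 50 h half-life and 36.5% at 110 h.

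The cost is one extra model run and table row per comparison, with no change to dosing, sampling or sample size. The report should note where AUC(0-t) ends at different times by treatment.
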